THE EFFECT OF PANCREATIC INSUFFICIENCY ON HYPOGLYCEMIA AND GLUCAGON RESPONSE IN CHILDREN WITH CYSTIC FIBROSIS

Short Running Title: Hypoglycemia and Glucagon Response in CF

[name],PhD ^{1,2} [name] [name] ¹ [name] [name] ² [name] ² [name] [name] ¹ [name] ¹ [name] ¹ [name] ³ [name] ³ [name] ³ [name], PhD ² [name] ¹

 ¹ Division of Pediatric Endocrinology and Diabetes, Department of Child Health and Disease, Marmara University School of Medicine, Istanbul, Turkey
² Department of Molecular Medicine, School of Health Science, Yeditepe University, Istanbul, Turkey

³ Division of Pediatric Pulmonogy, Department of Child Health and Disease, Marmara University School of Medicine, Istanbul, Turkey

Corresponding author: [name], [contact] [contact]

Date of document: 30/12/2022

STUDY PROTOCOL

1.Introduction

The exact underlying mechanism of hypoglycemia in CF is still unknown. Some recent studies support the delayed and prolonged insulin secretion and impaired counterregulatory hormone response as the reason of reactive hypoglycemia, whereas the others argued an additive effect of an intrinsic factor. However, the weakness of these limited studies is that nearly all of them included CF patients who had pancreatic insufficiency (PI) and could not reveal the mechanism of hypoglycemia seen in those without PI. In addition, there were no healthy controls for comparison of glucagon secretion in CF patients with hypoglycemia. Moreover, the studies that evaluate the role of glucagon in hypoglycemic CF patients were performed in hypoglycemic adult patients with abnormal glucose tolerance (AGT) and the delayed and prolonged insulin release is expected to be more likely as the reason of hypoglycemia in this setting. Previously, the investigators had demonstrated isolated hypoglycemia in some of the pediatric CF patients during OGTT. In this study, they further evaluated possible mechanisms of hypoglycemia. The investigators hypothesized that the mechanism of isolated hypoglycemia might be different from hypoglycemia seen in patients with AGT. Furthermore, they investigated the role of pancreatic insufficiency in hypoglycemia of CF patients by analyzing glucose, insulin and glucagon response to a glucose load in CF patients with an without PI.

2. Methods

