2.2. Procedures

A 3-h OGTT was performed in the morning following overnight fasting of ≥ 8 h. All participants (CF patients and controls) received oral glucose solution (1.75 g/kg; max: 75 g). Blood samples were collected at 0, 30, 60, 90, 120, 150 and 180 min for glucose and insulin, 0, 60, 120,150 and 180.min for glucagon measurement. HbA1c and CRP levels at baseline and cortisol levels at 0-180.min were also measured to assess the status of inflammation and body stress.

OGTT results were categorized into different subgroups of glucose tolerance according to ISPAD guidelines (12). Subjects who had INDET (Indeterminate Glucose Tolerance) or IGT (Impaired Glucose Tolerance) without hypoglycemia on OGTT were classified as Abnormal Glucose Tolerance (AGT). According to the IHSG position statement, hypoglycemia was defined in the presence of any venous glucose level is lower than 70 mg/dL (13). The terminology of "isolated hypoglycemia" (IsoHypo) was used for the participants who had hypoglycemia without AGT or CFRD and "Hypo+AGT" was used for the participants who had hypoglycemia with AGT. After the first analyses, the participants with IsoHypo and NGT were also sub-classified according to the presence of PI to evaluate the effect of PI on hypoglycemia (Figure-1).

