All analyses were carried out using GraphPad Prism® V5.0 software (GraphPad Software Inc., San Diego, California, USA). Variables are summarized for each group using descriptive statistics as percentages and mean \pm SD. Pairwise comparisons were performed using the Student T test or the Mann-Whitney U test depending on the data's normality. Kolmogorov-Smirnov test was used to evaluate of the data normality. Data were expressed as mean and standard error or deviation, which was stated. Statistical significance was set at *p* < 0.05.

THE EFFECT OF PANCREATIC INSUFFICIENCY ON HYPOGLYCEMIA AND GLUCAGON RESPONSE IN CHILDREN WITH CYSTIC FIBROSIS

Short Running Title: Hypoglycemia and Glucagon Response in CF

[name],PhD^{1,2} [name], MD¹ [name], PhD² [name], PhD² [name], MD¹ [name], MD¹ [name], MD¹ [name], MD³ [name], MD³ [name], MD³ [name], PhD² [name], MD¹

 ¹ Division of Pediatric Endocrinology and Diabetes, Department of Child Health and Disease, Marmara University School of Medicine, Istanbul, Turkey
² Department of Molecular Medicine, School of Health Science, Yeditepe University, Istanbul, Turkey

³ Division of Pediatric Pulmonogy, Department of Child Health and Disease, Marmara University School of Medicine, Istanbul, Turkey

Corresponding author: [name], [contact] [contact]

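### The hypothesis that isolated hypoglycemia differs in mechanism from hypoglycemia with AGT has only two-group tests behind it, and none of them separates an effect of AGT itself from a difference in what accompanies low glucose.

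*Combined protocol and SAP*

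**What the plan says.** The Introduction contains one sentence worded as a hypothesis: "The investigators hypothesized that the mechanism of isolated hypoglycemia might be different from hypoglycemia seen in patients with AGT". Just before it, on earlier studies in adults with AGT, the text says that "the delayed and prolonged insulin release is expected to be more likely as the reason of hypoglycemia in this setting".

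Section 2.2 supplies the groups. IsoHypo "was used for the participants who had hypoglycemia without AGT or CFRD"; Hypo+AGT "was used for the participants who had hypoglycemia with AGT". Children with INDET or IGT "without hypoglycemia on OGTT were classified as Abnormal Glucose Tolerance (AGT"). NGT appears as a further group when "the participants with IsoHypo and NGT were also sub-classified according to the presence of PI". Together these form a 2x2 layout in CF participants, hypoglycemia yes/no by abnormal tolerance yes/no.

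On inference, the Statistical Analysis Method section says: "Pairwise comparisons were performed using the Student T test or the Mann-Whitney U test depending on the data's normality", with the threshold at p < 0.05. It gives no regression, analysis of variance, interaction or named contrast, and no rule for deciding that two mechanisms differ. No summary measure or primary time point is named for insulin (seven samples) or glucagon (five samples).

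**The concern.** A natural statistical reading of the hypothesis is a comparison of two differences: what separates hypoglycemic from non-hypoglycemic children when tolerance is normal, against what separates them when it is abnormal. A two-group test can approach this in two ways, and each has a weakness.

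- **Direct test, IsoHypo versus Hypo+AGT.** The groups differ in tolerance status, which is assigned from the same OGTT. A hormone difference between them may belong to AGT and have nothing to do with the low glucose.
- **Two within-stratum tests, IsoHypo versus NGT and Hypo+AGT versus AGT.** One p-value below 0.05 and one above it do not show that the two differences differ.

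At stake is a claim that isolated hypoglycemia has its own mechanism, resting on a comparison that would often be significant if hypoglycemia were accompanied by the same hormone change in both strata. The reverse error, missing a real difference, is also possible. Multiplicity adjustment would help with neither, because it alters the p-values and leaves the contrasts as they are.

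**Working it through.** The plan states no sample size, SD, effect size or power, so there is no figure of its own to reproduce.

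**From the documents:** the four groups (section 2.2), two-group tests only, threshold 0.05 (Statistical Analysis Method). **Assumed:** two-sided tests, normal data with SD 1, equal groups of *n* = 10 to 20, hypoglycemia effect *h* = 0.8 SD in both strata, AGT effect *a* = 0.5 to 1.0 SD.

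**Step 1: what each contrast estimates.** The group means are NGT 0, IsoHypo *h*, AGT *a*, Hypo+AGT *a* + *h*.

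- Direct: (*a* + *h*) − *h* = *a*. This is the AGT effect alone.
- Interaction: [(*a* + *h*) − *a*] − [*h* − 0] = 0. This is correct, because the hypoglycemia effect is the same in both strata.
- If both hypoglycemic groups are referred to the same healthy controls, the control mean cancels and the direct contrast returns.

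**Step 2: how often each is significant at 0.05** (40,000 simulated studies per row).

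| *n* per group | *a* (SD) | Direct test | Within-stratum tests disagree | Interaction |
|---|---|---|---|---|
| 10 | 0 | 4.9% | 47.6% | 4.8% |
| 10 | 0.5 | 18.5% | 47.5% | 4.9% |
| 10 | 1.0 | 56.2% | 47.7% | 5.1% |
| 15 | 0.5 | 26.2% | 48.9% | 4.9% |
| 15 | 1.0 | 75.0% | 49.1% | 4.9% |
| 20 | 0 | 5.0% | 42.6% | 5.1% |
| 20 | 0.5 | 33.4% | 42.4% | 5.0% |
| 20 | 1.0 | 87.1% | 42.3% | 5.0% |

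The disagreement rate follows from 2*p*(1 − *p*), where *p* is the power of each within-stratum test. At *n* = 10, *p* = 0.392 and 2 × 0.392 × 0.608 = 0.477. At *n* = 20, *p* = 0.694 and 2 × 0.694 × 0.306 = 0.425.

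**Step 3: sensitivity.** With *a* = 0.2 SD the direct test is significant in 7% to 9% (*n* = 10 to 20). Disagreement is about 9.5% when *h* = 0, and falls to 0.8% at *h* = 1.5 SD with *n* = 20.

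**Step 4: the reverse error.** Let hypoglycemia add 1 SD only without AGT, and let AGT itself add 1 SD. The means are 0, 1, 1, 1. The direct contrast is 0, and its test is significant in 5%. The interaction is (1 − 1) − (1 − 0) = −1, detected in 33%, 48% and 60% at *n* = 10, 15 and 20.

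**Step 5: what the interaction costs.** With equal groups its standard error is √(4/*n*) against √(2/*n*) for a pairwise difference, a ratio of √2 ≈ 1.4. With assumed groups of 30 (NGT), 15 (IsoHypo), 20 (AGT) and 5 (Hypo+AGT), the ratio to the IsoHypo − NGT error is √(1/30 + 1/15 + 1/20 + 1/5) / √(1/30 + 1/15) = √(0.35/0.10) ≈ 1.9. For 80% power at 1.0 SD, the interaction needs 32 per group against 16 for a pairwise difference.

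**Step 6: scale.** With lognormal data (assumed log-SD 0.5 to 0.8), equal proportional effects in both strata (0.8 SD hypoglycemia, 1.0 SD AGT on the log scale) and *n* = 10 to 20, the raw-scale interaction rejects in 8% to 16%. On the log scale it stays at 5%.

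**The case against.** The strongest objection concerns what counts as mechanism. The Introduction treats late insulin as the likely cause of hypoglycemia in AGT, which is more than a background feature of AGT. If so, late insulin that is high in Hypo+AGT and absent in IsoHypo supports the hypothesis, and the direct comparison is relevant. Suppose late insulin is raised by *a* in all children with AGT but only some become hypoglycemic. The means are 0, 0, *a*, *a*; the interaction on insulin is *a* − *a* − (0 − 0) = 0, although the mechanisms differ. This stands. A reader might infer that the interaction is the only valid basis for a claim. The documents name no contrast and do not support that, and relying on it alone could subtract out the mechanism proposed.

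Second, the plan names no pairs and no decision rule. A reader might infer that the trial will read one significant and one non-significant test as a difference, or will probably reach a false conclusion. Nothing in the documents says so. The disagreement figures describe an inference that the plan leaves open.

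Third, a reader might infer that pairwise tests report a different mechanism whenever the mechanism is the same. They do not: the direct test holds about 5% if AGT does not affect the variable. The Introduction's expectation concerns insulin; no AGT effect on glucagon is documented.

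Fourth, the hypothesis is tentative, and the title and the sub-classification centre on pancreatic insufficiency. This bears on severity. It does not supply a test for the hypothesis.

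**Conclusion.** The concern holds in a limited form. No test in the plan separates an AGT effect on the hormone from a difference in what accompanies hypoglycemia, and the plan does not say which comparison bears on its hypothesis. Where hypoglycemia has the same effect in both strata, the direct test is significant in 19% to 87% of studies and the within-stratum tests disagree in 42% to 49%, against about 5% for the interaction. These ranges rest on assumed groups of 10 to 20, a 0.8 SD hypoglycemia effect, AGT shifts of 0.5 to 1.0 SD and normal data, none of which the documents give. This is a gap in the plan and does not show that a wrong conclusion was drawn. It should be fixed, but it does not invalidate the study.

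**What to change.** State in the SAP which comparisons address the hypothesis, and add one analysis in CF participants:

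- Fit a two-factor model, hypoglycemia yes/no by AGT yes/no, on one named late insulin summary and one named glucagon summary, log-transformed if skewed. For this factor, AGT must mean INDET or IGT whether or not hypoglycemia occurred; section 2.2 reserves the bare label for children without it.
- Exclude any CFRD first found on the study OGTT, or place it by a stated rule.
- Report the interaction with its 95% CI, labelled exploratory, beside the direct IsoHypo versus Hypo+AGT difference and the AGT versus Hypo+AGT difference. The last shows whether the hormone distinguishes hypoglycemic from other children within AGT, which matters if late insulin is the proposed cause there.
- Do not infer a different mechanism from one pairwise test being significant and the other not, or from the direct test alone. If the interaction CI is wide, say that the data do not distinguish the two.

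The cost is SAP wording and one model per summary on data already collected. The downside is precision: the interaction has about 1.4 times the standard error of a pairwise difference with equal groups, and more with unequal ones, so it may be inconclusive.

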2.1. Participants

Children and adolescents aged 10-18 years with CF who were regularly followed-up at the Pediatric Pulmonology and Endocrinology Units, between January 2020 and December 2020 were invited to participate in the study before their annual OGTT. Pancreatic insufficiency (PI) was defined by need for enzyme replacement therapy based on clinical symptoms or fecal elastase level ($<200 \ \mu g/g$). Individuals using corticosteroid therapy, those who had acute exacerbation in the last 3 months or previously diagnosed with diabetes were not eligible. Height, weight, BMI, FEV1, genetics and the presence of PI of the participants were recorded.

The control group included age-matched healthy, non-diabetic siblings of patients with type 1 diabetes who were followed-up at our clinic. All the controls were negative for β -cell autoantibodies (anti-glutamic acid decarboxylase, islet cell antibody, and insulin antibody). The study protocol was approved by the Marmara University Ethics Committee (no:09.2019.933), and written informed consent was obtained from the parents and the participants.

2.2. Procedures

A 3-h OGTT was performed in the morning following overnight fasting of ≥ 8 h. All participants (CF patients and controls) received oral glucose solution (1.75 g/kg; max: 75 g). Blood samples were collected at 0, 30, 60, 90, 120, 150 and 180 min for glucose and insulin, 0, 60, 120,150 and 180.min for glucagon measurement. HbA1c and CRP levels at baseline and cortisol levels at 0-180.min were also measured to assess the status of inflammation and body stress.

OGTT results were categorized into different subgroups of glucose tolerance according to ISPAD guidelines (12). Subjects who had INDET (Indeterminate Glucose Tolerance) or IGT (Impaired Glucose Tolerance) without hypoglycemia on OGTT were classified as Abnormal Glucose Tolerance (AGT). According to the IHSG position statement, hypoglycemia was defined in the presence of any venous glucose level is lower than 70 mg/dL (13). The terminology of "isolated hypoglycemia" (IsoHypo) was used for the participants who had hypoglycemia without AGT or CFRD and "Hypo+AGT" was used for the participants who had hypoglycemia with AGT. After the first analyses, the participants with IsoHypo and NGT were also sub-classified according to the presence of PI to evaluate the effect of PI on hypoglycemia (Figure-1).

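### The tolerance groups are cut from the glucose of the same OGTT that supplies the outcomes, so glucose p-values between them are circular and unadjusted insulin p-values cannot by themselves show a mechanism

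*Combined protocol and SAP*

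**What the plan says.** **Groups.** Section 2.2 states: "OGTT results were categorized into different subgroups of glucose tolerance according to ISPAD guidelines (12". In the same section, "hypoglycemia was defined in the presence of any venous glucose level is lower than 70 mg/dL (13". AGT means INDET or IGT without hypoglycemia. IsoHypo means hypoglycemia without AGT or CFRD. Hypo+AGT means both. All four groups, NGT included, come from the glucose values of one test.

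**Outcomes.** The same test provides them: "Blood samples were collected at 0, 30, 60, 90, 120, 150 and 180 min for glucose and insulin". Only concentrations are listed. There is no insulin index, timing measure, repeat OGTT or independent classification.

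**Analysis.** The Statistical Analysis Method states: "Pairwise comparisons were performed using the Student T test or the Mann-Whitney U test depending on the data's normality". It adds: "Statistical significance was set at *p* < 0.05". It names no variables, group pairs, time points or covariates.

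**Question.** The Introduction hypothesises that isolated hypoglycemia may differ in mechanism from hypoglycemia in patients with AGT. Of the latter it says that "the delayed and prolonged insulin release is expected to be more likely as the reason of hypoglycemia in this setting".

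**The concern.** If two groups are separated by their glucose values, a test of those values returns the grouping rule and is not a finding. Insulin is one step removed. It responds to glucose, so children chosen for high or low glucose tend to have different insulin even if their beta cells respond to glucose in the same way. A raw insulin concentration at a clock time does not separate altered secretion from insulin that simply follows the glucose used for selection.

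The mechanism hypothesis compares IsoHypo with Hypo+AGT, and both are defined this way. A significant insulin difference at 120 or 150 min could be read as evidence of delayed or prolonged release when it reflects selection.

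**Working it through.** The documents give no sample size, SD, effect size or power, so there is no figure to reproduce. The only design number is the 0.05 level (two-sided assumed). The check asks how often insulin would differ if there were no secretory difference.

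**Step 1. Closed form at one time point.** Assumptions, none from the documents: 120-min glucose has mean 125 and SD 30 mg/dL, the cut is at 140, insulin has correlation ρ with glucose, and equal groups are compared by t test.

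- Cut in SD units: (140 − 125)/30 = 0.5.
- Mean glucose above the cut: 0.352/0.309 = 1.141 SD. Below it: −0.352/0.691 = −0.509 SD. Gap: 1.650 SD.
- Within-group glucose variances: 0.268 above and 0.486 below, average 0.377.
- Standardised insulin gap: d = 1.650ρ / √(0.377ρ² + 1 − ρ²). Noncentrality: d√(n/2).

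| ρ | d | Rejection, n = 8 per group | n = 20 per group |
|---|---|---|---|
| 0 | 0 | 5% | 5% |
| 0.2 | 0.334 | 10% | 18% |
| 0.4 | 0.696 | 25% | 57% |
| 0.6 | 1.124 | 55% | 93% |

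Simulation gives 4%–6%, 10%–18%, 24%–57% and 56%–94% for the four rows, which agrees. Testing glucose itself is the case ρ = 1: d = 2.687, with rejection in about 100% of studies from n = 8 upward.

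**Step 2. A full 180-min test with feedback.** Every child has the identical law linking insulin secretion to glucose. Only insulin sensitivity, glucose absorption or both vary. There are seven samples, as in section 2.2. Groups use the stated rule of below 70 mg/dL plus assumed cut-offs: IGT at 120-min glucose 140–199, and INDET at mid-test glucose of 200 or more with 120-min glucose below 140. There were 800 draws per setting. AGT versus NGT:

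| What varies (secretion slope) | 120-min insulin test rejects, n = 10 to 20 | Mean 120-min insulin, AGT vs NGT | Mean insulin peak (min), AGT vs NGT | Time-to-peak test rejects |
|---|---|---|---|---|
| Both (0.6) | 44% to 76% | 47 vs 37 | 84.7 vs 79.5 | 7% to 12% |
| Both (0.8) | 44% to 64% | 54 vs 42 | 81.1 vs 76.4 | 8% to 9% |
| Both (1.2) | 31% to 54% | 61 vs 45 | 75.7 vs 71.7 | 5% to 10% |
| Both, wider (0.8) | 66% to 95% | 57 vs 36 | 83.9 vs 79.7 | 7% to 10% |
| Sensitivity only (0.8) | about 100% | 71 vs 38 | 86.0 vs 69.9 | 52% to 86% |
| Absorption only (0.8) | 57% to 85% | 37 vs 48 | 71.9 vs 84.0 | 18% to 44% |

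In the first three rows, at least one of the seven times is significant in 75%–78% of studies at n = 10 and 94%–98% at n = 20. Seven independent null tests would give 1 − 0.95⁷ = 30%.

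The last row shows the sign reversing: AGT insulin is lower at 120 min and peaks earlier. If the insulin curves are literally identical, rejection is 3%–6% per time point after baseline and 5% for time to peak.

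**Step 3. Hypo+AGT.** In most settings this group's insulin peaked earlier than in NGT (48–71 min). The exception was sensitivity-only variation, where the group was about 0.1% of children.

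**Step 4. Candidate remedies under one secretion law.**

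- *Late insulin adjusted for concurrent glucose.* If insulin is generated as a function of concurrent glucose, adjustment returns 5%–6% in most contrasts, but that is largely built in. In a feedback model with lagged insulin (12 per group, 400 draws), adjusted AGT versus NGT stayed at 2%–7% when sensitivity varied. With sensitivity-only variation, adjusted IsoHypo versus NGT rejected 26%–64% at 120–180 min, where the raw test rejected 5%–10%. With absorption-only variation, adjusted AGT versus NGT rejected 76% at 180 min. A separate crude feedback model gave raw rejection of 51%–100% for IsoHypo versus NGT at 120–150 min, and adjusted rejection of 35%–77% in some contrasts.
- *Early insulin rise per early glucose rise (0–30 min).* In that last model it rejected 5%–22% in most contrasts and 33% in one.
- *Incremental insulin area over incremental glucose area.* It rejected 3%–9% for AGT versus NGT in the Step 2 model, but 97%–100% if insulin curves are identical.

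**The case against.** **Tested quantity.** The analysis text names no variables, so testing raw insulin between these groups is inferred. This stands as a limit. However, concentrations are all that is listed and unadjusted tests are all that is offered, so following the plan as written leads there.

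**Delayed insulin in AGT.** A reader might infer that the plan will falsely show delayed insulin in AGT. The documents do not support this. The Introduction attaches delayed release to hypoglycemia in patients with AGT, whereas section 2.2 defines the AGT group as free of hypoglycemia. Nor do the simulations show it generally. The usual artefact is raised late insulin, time to peak seldom rejects unless sensitivity alone varies, and the sign reverses under absorption-only variation.

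**Bias towards the hypothesis.** A reader might also infer that the errors favour the hypothesis that the two forms of hypoglycemia differ. That is not shown. The direction depends on why glucose differs, and Hypo+AGT usually peaked early rather than late.

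**Adjustment as the cure.** Step 4 shows that conditioning on concurrent glucose can create differences. Insulin also lowers glucose and lags it, so the adjustment partly conditions on a consequence.

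**Scope.** CF versus healthy controls, and PI versus non-PI, are not defined by OGTT glucose, and the point does not reach them where the compared groups are unselected on glucose. IsoHypo versus NGT within a PI stratum keeps the problem.

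**Conclusion.** The point holds in limited form. The circularity of glucose p-values between NGT, AGT, IsoHypo and Hypo+AGT follows from the definitions and needs no physiological assumption.

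For insulin, the conclusion is that an unadjusted p-value cannot identify a secretory mechanism, because rejection well above 5% occurs in either direction under one shared secretion law. The illustrative size is 31%–76% at 120 min for AGT versus NGT, and more when sensitivity and absorption vary more widely or sensitivity alone varies. It rests on assumed cut-offs, 10 to 20 children per group, assumed kinetics and secretion slopes of 0.6–1.2. It falls to the nominal level if insulin curves are identical.

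The data remain sound. What is unsupported is a claim of delayed or prolonged insulin, or of a different mechanism in IsoHypo than in Hypo+AGT, resting on these p-values alone.

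**What to change.** In the Statistical Analysis Method:

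1. State that glucose is described, and not tested, between groups defined by OGTT glucose.
2. Label raw clock-time insulin comparisons between these groups as descriptive.
3. Add two per-child measures from the existing samples: early insulin rise divided by early glucose rise (0–30 min), and time of insulin peak minus time of glucose peak. State how a child with little or no 30-min glucose rise is handled. Note that samples 30 min apart resolve peak times only coarsely. The peak-difference measure itself was not simulated here.
4. Limit mechanism conclusions to what these measures support, and say that groups were selected on glucose from the same test.
5. Keep late insulin adjusted for concurrent glucose as a sensitivity analysis at most.

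The cost is SAP wording and re-analysis of data already collected. The downside is small: fewer formal p-values, and indices that are less prone to the artefact but not immune to it.

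### The IsoHypo versus Hypo+AGT comparison takes no account of pancreatic insufficiency (PI), so a difference in PI share between the groups could appear as, or hide, a difference in mechanism

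*Combined protocol and SAP*

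**What the plan says.** The Introduction contains one statement worded as a hypothesis: "The investigators hypothesized that the mechanism of isolated hypoglycemia might be different from hypoglycemia seen in patients with AGT". It then adds a second question on PI: "they investigated the role of pancreatic insufficiency in hypoglycemia of CF patients by analyzing glucose, insulin and glucagon response to a glucose load". Section 2.1 confirms that the variable is available: "Height, weight, BMI, FEV1, genetics and the presence of PI of the participants were recorded".

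Section 2.2 forms the groups from the OGTT. IsoHypo is hypoglycemia without AGT or CFRD, and the Hypo+AGT label "was used for the participants who had hypoglycemia with AGT". PI is part of neither definition. The PI split comes later and is limited: "After the first analyses, the participants with IsoHypo and NGT were also sub-classified according to the presence of PI". Its stated purpose is to evaluate the effect of PI on hypoglycemia.

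On method, the Statistical Analysis Method says: "Pairwise comparisons were performed using the Student T test or the Mann-Whitney U test depending on the data's normality". The threshold is given as "Statistical significance was set at *p* < 0.05". No model, covariate, stratification or matching on PI is described.

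**The concern.** The plan treats PI as something that may change insulin and glucagon after a glucose load. A variable of that kind confounds a comparison of two hypoglycemia groups whenever its share differs between them. Membership of IsoHypo or Hypo+AGT depends on glucose tolerance, and nothing in the design keeps the PI shares alike.

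Suppose the hormone response is the same in both groups among children with PI, and the same in both groups among children without PI. If one group has more PI, the group means still differ, and a two-sample test can report this as a difference between the two types of hypoglycemia. If the imbalance runs the other way, it can mask a real difference. Because Hypo+AGT is left out of the PI split, a reader of the results may be unable to tell which case applies.

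**Working it through.** **Plan's own figure.** There is none to reproduce. The documents state no sample size, power, SD, effect size, group counts or PI shares. Everything below except the 0.05 threshold is an assumption, and two-sided testing is also assumed.

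**Bias.** Write p₁ and p₂ for the PI shares in IsoHypo and Hypo+AGT, and δ for the PI effect on the hormone in SD units. With no true group difference at a given PI status, the expected unadjusted difference is (p₂ − p₁) × δ.

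- Shares 50% and 90%: 0.40 × 0.5 = 0.20 SD; 0.40 × 0.8 = 0.32 SD; 0.40 × 1.2 = 0.48 SD.
- Shares 70% and 90%: 0.20 × 0.5 = 0.10 SD; 0.20 × 0.8 = 0.16 SD; 0.20 × 1.2 = 0.24 SD.
- Equal shares: 0 for any δ.

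**False-positive rate of the planned t test.** This was simulated with normal errors (SD 1), PI drawn at the assumed shares and no true group difference:

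| PI shares | n per group | δ = 0.5 | δ = 0.8 | δ = 1.2 |
|---|---|---|---|---|
| 50% vs 90% | 10 | 7% | 10% | 15% |
| 50% vs 90% | 20 | 9% | 15% | 26% |
| 50% vs 90% | 30 | 12% | 21% | 37% |
| 70% vs 90% | 10 | 5–6% | 6% | 8% |
| 70% vs 90% | 20 | 6% | 8% | 10% |
| equal | 10 to 30 | 5% | 5% | 5% |

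**Mann-Whitney U test.** Switching to the rank test does not help. With shares of 50% and 100% and δ = 1.0, the bias is 0.50 × 1.0 = 0.50 SD. The t test then rejects 16.9%, 30.9% and 44.0% of the time at 10, 20 and 30 per group, and the Mann-Whitney test 14.7%, 29.2% and 41.0%.

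**With PI in the model.** A linear model of response on group and PI, run at shares of 80/80%, 60/90% and 50/100% with δ from 0.5 to 1.5, rejects 4.2% to 6.2% of the time. The nominal rate is 5% and the simulation error is about 0.5 points.

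**Price of adjusting.** Take 20 per group, a true difference of 0.9 SD and no PI effect. Power goes from about 80% to 78% with equal shares, and from about 79% to 69% at 50% versus 90%. Restricting to children with PI leaves 0.5 × 20 = 10 against 0.9 × 20 = 18. The noncentrality is 0.9 × √(10 × 18 / 28) = 2.28 on 26 degrees of freedom, which gives power of about 59%.

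**The case against.** The strongest objection is that PI may be part of the answer. If Hypo+AGT differs from IsoHypo because more of those children have PI, that is a finding about mechanism. The unadjusted and adjusted differences answer different questions. This stands, and it is why the adjusted result belongs beside the unadjusted one and should not replace it.

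Second, nothing in the documents shows an imbalance. With similar shares there is no inflation, and at 10 per group or a small PI effect it is modest. This also stands.

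Third, adjustment is weakest where the bias is largest. If nearly all Hypo+AGT children have PI, the PI coefficient comes almost entirely from IsoHypo and relies on PI acting equally in both groups. That is a reason to use the within-PI comparison in that case, not a reason to ignore PI.

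A reader might infer four stronger points that the documents do not support:

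- *That both groups mix children with and without PI.* The definitions allow it, but the PI make-up of Hypo+AGT is not given. All of those children may have PI, which might explain why the group was not split. Figure-1, which is not shown, may give counts. The confounding would remain in that case, with a mixed IsoHypo group set against an all-PI group.
- *That this is the main or primary comparison.* No primary hypothesis or endpoint is named, the title puts PI first, and this pair is only implied by the reference to pairwise comparisons.
- *That a comparison of all hypoglycemic CF children with healthy controls has the same fault.* Section 2.2 keeps IsoHypo and Hypo+AGT separate, and no pooled comparison with controls is described.
- *That the study repeats the weakness it criticises in earlier work.* The criticism is narrower: "nearly all of them included CF patients who had pancreatic insufficiency (PI) and could not reveal the mechanism of hypoglycemia seen in those without PI". Including children without PI and splitting IsoHypo and NGT by PI answers it.

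**Conclusion.** The point holds as a gap in the analysis plan, not as a demonstrated bias. The text establishes that the two hypoglycemia groups are formed without regard to PI, that the PI split does not name Hypo+AGT, and that the only tests described cannot adjust. A difference in PI share would therefore enter the contrast behind the stated hypothesis, in either direction.

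Its size depends wholly on quantities the documents do not give. An imbalance of 40 percentage points with a PI effect of 0.8 SD or more would matter at 20 per group (15% or more false positives against a nominal 5%). An imbalance of 20 points at the same size would matter little to moderately (6% to 10%). These rates assume normal errors, equal group sizes and a PI effect that is the same in both groups. Because PI is already recorded and the remedy is cheap, the change is worth making even though the imbalance is unknown.

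**What to change.** 1. Extend the PI sub-classification to Hypo+AGT, and report the PI count in every CF group.
2. Keep the unadjusted IsoHypo versus Hypo+AGT comparison. Beside it, report the difference adjusted for PI (yes/no) from a linear model, on the log scale if the hormone is skewed, with its 95% CI.
3. Show the same comparison within children with PI.
4. If few or no Hypo+AGT children are without PI, use the within-PI comparison and limit the mechanism conclusion to children with PI.
5. State that the unadjusted difference includes any contribution of PI and the adjusted one removes it, so that readers do not treat them as rival answers to one question.

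The cost is SAP and reporting wording plus one covariate already in the data; no further patients or samples are needed. Precision is lower for the adjusted difference when PI and group overlap, and lower again for the within-PI comparison. Both should be read from their intervals, and a non-significant adjusted result should not be taken as evidence of a shared mechanism.
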